## 4.4 Packaging and Labeling

#### **4.4.1** Lenses

The site is responsible for ordering all habitual contact lenses needed for the study and submitting an invoice for reimbursement. Three pairs of the subject's habitual contact lenses will be provided for each subject; two pairs will be dispensed to the subject at the Screening/Dispensing Visit (one to wear and one for back-up). The third pair will be retained in-office in the event that a non-scheduled replacement is required. Additional lenses should be ordered if the third pair is dispensed.

### 4.4.2 Study Kits

The Sponsor will provide Study Kits for each subject. All Study Kits will be assigned by the ORS randomization system and distributed to the subject by the unmasked designee. Each Study Kit will include the following materials:

• Either 56 pouches containing 5 single-use dispensers of BL-300-PFM04 Preservative Free Lubricating and Rewetting Drops (Test) or six bottles of OPTI-FREE Replenish Rewetting Drops (Control). The drops will be enclosed in a white carton. Each carton, bottle or pouch will be labeled with an investigational label including the Study Kit number (a unique 5-digit number). One randomized Study Kit will be provided to subjects at the Screening/Dispensing Visit. The subject number may be written on the outside carton ONLY. The rewetting drops should not be written on or labelled.

## 4.4.3 Other Study Supplies

The following will be stored at the sites to be provided to subjects:

- One 10 FL. OZ. bottle of Bausch + Lomb Biotrue multi-purpose solution.
  - -or-
- Three 3.5 FL OZ bottles of Boston SIMPLUS Multi-Action Solution.
- Lens case. Subjects are required to use the supplied lens cases. In the event of replacement lenses, use a lens case to store the lens(es).

- **Zippered Bag.** To hold empty multi-dose rewetting drop bottles or opened single-use dispensers.
- Subject Instructions. Will be provided at Screening/Dispensing visit.

### 4.5 Return of Study Materials

Each subject will have one opaque Subject ID sealable bag for return of all materials.

- Study Kit Return Materials. The unmasked designee will place all the subject's Test or Control articles (Study Kit with unopened multi-use bottles or single-use dispensers, partially full, and empty multi-use bottles or single-use dispensers) into an opaque Subject ID sealable bag along with worn/unworn lenses as described below. Do not seal the bag until full accountability at the study close out visit with the monitor is complete. It is not necessary to return the Biotrue multi-purpose solution or Boston SIMPLUS Multi-Action Solution bottles or unused lens cases.
- Lens Return Materials. The unmasked designee will place worn lenses in a lens case filled with Bausch + Lomb Sensitive Eyes Saline Solution. Complete a worn lens label provided for each lens case returned with identifying information such as study number, site identification number, subject number, subject initials, lens type, date dispensed, date removed, quantity of lenses returned (which should be one lens for each eye) and adhere the label to zippered bag. If replacement lenses were used, use a separate lens case and zippered bag with identifying information. Place the zippered bag(s) containing the lens case(s) into the opaque Subject ID sealable bag with any unworn lenses and all Study Kits as described above. Do not seal the bag until full accountability at the study close out visit with the monitor is complete.

Use the supplied pre-printed FedEx labels for return of the study materials to the Sponsor after close out visit.

### 4.6 Accountability

The Unmasked Designee at each site will be responsible for keeping current and accurate records of the amount of single-use dispensers or bottles received and dispensed, and its disposition. The single-use dispensers or bottles must be stored under the appropriate conditions in a secure area and are to be dispensed only to subjects enrolled in the study, in accordance with the conditions specified in this protocol. During the course of the study, the Investigator must account for all lenses and rewetting drops received, dispensed, and returned. A Product Accountability Log (PAL) will be provided to the sites for rewetting drops and a Lens Accountability Log (LAL) will be provided for lenses.

The Unmasked Designee will instruct the subject to bring their Study Kit (i.e., white carton originally containing 56 pouches of 5 single-use dispensers or 6 multi-use bottles) to the 1-Month visit and will collect all study materials (Study Kit and lenses dispensed or provided to the subject) only at the final/exit study visit. Study materials will not be collected at any other visit than the final/exit visit.

At time points throughout the study and/or upon completion of the study, the Sponsor/Sponsor's representative will review and verify the Investigator's accountability records. Following verification, and as directed by the Sponsor, all Study Kits (Test and

Control) and lenses (worn and unworn) must be returned to the Sponsor at the address below using the study supplied pre-printed FedEx labels.

Bausch & Lomb Incorporated Clinical Trial Materials Supply Chain, Area 56 [name]

### 4.7 Masking/Unmasking

This study is masked, therefore, the Investigator/site staff, subjects, and Bausch + Lomb personnel or designee(s) involved in the collection of study data will be masked to the study rewetting drops. Each site must have an unmasked designee that will be responsible for dispensing and accountability. This designee shall not participate in study assessments that may cause bias to the study data. Study Monitors should ensure that the unmasked designee is documenting accountability throughout the study, and should perform only accountability tasks during study that ensures they remain masked. (e.g. verify kit #, logs are present and being completed). Full accountability should be performed at study end.

The randomization schedule will be created by an unmasked statistician not otherwise involved in the study. Personnel involved with repackaging of clinical trial material will also be unmasked. Unmasked designees at the site will manage the dispensation and return of study rewetting drops and related supplies. All other study personnel will remain masked until database lock. Another research staff member may manage the dispensation of the habitual lenses.

Study rewetting drops will be provided in sealed opaque cartons with Study Kit numbers pre-printed on them. Although the Test and Control bottles/single-use dispensers will be visibly different, attempts will be made to mask the subjects by providing identical investigational labels and packaging identical kit cartons. Subjects will be instructed to place the drops in the eye and blink out of the sight of the Investigator or site staff. Subjects are not to show the study bottles/single-use dispensers to the Investigator or site staff unless instructed to do so.

If unmasking of a subject's randomly assigned treatment is required, the Investigator (or other designee) is required to attempt to contact the Medical Monitor to request permission to unmask. If this attempt is successful, then the Medical Monitor will contact the Sponsor designee (see Personnel and Facilities, Page 3) and obtain approval to grant permission to unmask. Upon receipt of authorization from the Sponsor designee, the Medical Monitor will advise the Investigator (or another qualified designee) to log into the randomization system and unmask the subject. If the Medical Monitor cannot be contacted, the Investigator (or other qualified designee) should attempt to contact the Sponsor designee who can authorize the unmasking of a subject. If the Medical Monitor or Sponsor designee cannot be contacted and the Investigator (or other qualified designee) deems the unmasking to be an emergency, the Investigator may log into ORS without authorization and unmask the subject. Whether unmasking occurs inadvertently or intentionally, the Investigator must notify the Medical Monitor or Sponsor designee as soon as possible after unmasking. In addition, the Investigator must record the date, time, and reason for unmasking the study treatment in the source documentation.

### 4.8 Product Replacement

Any additional/replacement (in the case of loss or damage) Test or Control rewetting drops must be ordered through the randomization system.

A back-up pair of lenses for each dispensed subject will be retained in-office in case a non-scheduled lens replacement is required, and the subject already used the two sets of lenses that were dispensed at the Screening/Dispensing Visit.

### 4.9 Risk Assessment

Information concerning potential risks associated with the investigational device (as well as possible interactions with concomitant medical treatments and risk-to-benefit ratio) can be found within the Investigator's Brochure (IB)/Report of Prior Investigations (ROPI) for the study. Risks are also summarized within the Informed Consent document. The assessments required for the study are routinely performed and are standard of care for contact lens wearers. The subjects will be informed of any potential study specific risks in the ICF or if new risks become apparent during the study.

### 5.0 SAFETY AND EFFECTIVENESS VARIABLES

Safety and effectiveness endpoints are also shown in Section 8.1.

### 5.1 Safety Variables

The safety of the rewetting drops will be determined by the following parameters:

- The primary safety endpoint will be slit lamp findings greater than grade 2.
- Adverse Events will also be evaluated. Information regarding any subject- or investigator- reported AEs will be obtained at each follow-up visit. The rate of adverse events is not a primary endpoint and is not associated with a predefined success criterion.

## **5.2** Primary Effectiveness Variables

Effectiveness of the rewetting drops will be determined by the following parameters:

- Overall comfort
- Dryness

### 5.3 Risk Assessment

The assessments required for the study are routinely performed and are standard of care for contact lens wearers. The subjects will be informed of any potential study-specific risks in the ICF or if new risks become apparent during the study. Upon review of the clinical and preclinical data, no additional risks were identified over the standard contact lens and care solution use.

### 6.0 STUDY METHODS

### 6.1 Study Visits

Refer to APPENDIX A: for a schedule of visits and parameters and APPENDIX B: for methods of clinical evaluation.

Prior to enrollment into the study, the Investigator (or designee) will explain the purpose of the study, procedures, risks/benefits, and subject responsibilities to the potential participant. The subject's willingness and ability to meet the follow-up requirements of the study will be determined. If the subject chooses to participate in the investigation, written informed consent, including Health Insurance Portability Accountability Act (HIPAA) authorization, will be obtained. The subject and the person obtaining written consent will sign and date the IRB-approved ICF. The Investigator should retain the signed original document in the subject's record and provide a copy to the subject. In addition, the applicable privacy regulation requirements must be met.

### 6.1.1 Screening/Dispensing Visit

After obtaining written informed consent, prospective subjects will be screened to determine whether they meet the entry criteria for the study.

A Screening and Enrollment Log will be provided by the Sponsor to track all consented subjects that the Investigator interviews regarding the study and completed study visits for enrolled subjects. Once the Screening and Enrollment Log is complete and all data is reviewed and confirmed by the field monitor, the Investigator will sign and date the form verifying the documented data is correct. The Investigator will retain a copy of the original document for their records and the field monitor will submit the original for Sponsor.

After obtaining written informed consent, prospective subjects will be screened to determine whether they meet the entry criteria for the study.

The Screening/Dispensing Visit will proceed as follows:

NOTE: All VA measurements MUST be made using a phoropter.

- a. Enter the subject information on the next available line of the Screening Log.
- b. Collect demographic and medical history (within 1 year of signing the ICF) and concomitant medications. Concomitant medications (as defined for this study) include any medications (systemic and ocular) for conditions taken within 30 days of signing the ICF.
- c. Collect the following baseline lens/lens care history information and lens wear parameters from the subject:
  - Average number of days per week worn
  - Average daily wearing time, hours per day
  - Average hours of comfortable wear per day
  - Hours lenses worn on the day of this visit
  - Current lens brand, sphere power, base curve and diameter
  - Current lens care products
- d. Perform the following baseline assessments (without lenses; remove the lenses if the subject wore lenses to the visit):
  - Spherocylindrical refraction
  - High contrast distance best spectacle-corrected visual acuity (BSCVA)
  - Keratometry
- e. Perform a slit lamp examination (without lenses) and record:

- Any ungraded finding marked as "Present"
- Any corneal scars
- Any neovascularization within the central 6 mm of the cornea
- Any corneal staining
- Any corneal infiltrate (record details on the APPENDIX C: Corneal Infiltrates Evaluation Form)
- Record and sketch any scars and slit lamp findings greater than Grade 2 in the subject's source document.
- f. Indicate on the Screening and Enrollment Log whether the subject is a "Screen Pass" or "Screen Fail." Only "Screen Pass" subjects should be randomized in the study. "Screen Fail" subjects are ineligible and cannot be randomized in the study. No eCRFs shall be completed for "Screen Fail" subjects.
  - If the subject is a "Screen Pass": Log into ORS to randomize the subject. Enter the subject number from ORS on the Screening and Enrollment Log.
  - If the subject is a "Screen Fail": Log into ORS and indicate the reason for screen failure. Enter the subject number from ORS on the Screening and Enrollment Log.
- g. If the subject is a "Screen Pass" the Unmasked Designee should then dispense the randomized Study Kit (refer to Section 4.4.2) to the subject and record the required information in the subject's individual Product Accountability Log.
- h. Dispense two pairs (one for back up only) of the subject's habitual contact lenses and record on the Lens Accountability Log.
- i. Instruct subject to insert study lenses and collect the following Subjective Assessments for the insertion of study lenses using the 0-100 rating scales:
  - Burning/Stinging Upon Insertion (Rating Scale #1)
  - Comfort Upon Insertion (Rating Scale #2)
  - Ease of Handling/Insertion (Rating Scale #5)
- j. Unmasked designee will instruct, and view the subject placing 1-2 study rewetting drops in each eye and blinking. Within 1 minute, collect the following Subjective Assessments for the instillation of study drops using the 0-100 rating scales:
  - Burning/Stinging Upon Drop Instillation (Rating Scale #16)
  - Comfort Upon Drop Instillation (Rating Scale #17)
  - Vision Upon Drop Instillation (Rating Scale #18)
- k. Record the following into the subject's source documentation for entry in to EDC:
  - Dispensed lens type (brand), sphere power, base curve and diameter
  - High contrast distance lens VA
  - Over-refraction and distance VA
  - Lens wettability
  - Lens centration
  - Lens movement
  - For each eye, compare the high contrast distance lens VA to the high contrast Distance Best Spectacle-Corrected VA obtained at this visit. If the VA has decreased by 5 letters (0.1 logMAR) or more, explain.

- 1. The Unmasked Designee will explain to the subject that:
  - Study Kit cartons and its contents are NOT to be opened in front of any other site personnel.
  - The subject should retain all study materials (bottles/single-use dispensers and lenses) during the course of the study.
  - Prior to coming to the site for the 1-month, exit or early study termination visits, the subject should: (i) place zippered bag containing all used single-use dispensers or multi-dose bottles and unused single-use dispensers/bottles of study rewetting drops into their original white carton, (ii) place the carton and all lens cases into the opaque subject take-home white drawstring bag, (iii) close the bag, and (iv) return it to the unmasked designee.
- m. The Unmasked Designee can dispense the Other Supplies, as needed by the patient (refer to Section 4.4.3).
- n. If the Subject was randomized and needs to be exited during this visit, complete the Exit Visit as per Section 6.1.4.
- o. Collect/assess all AEs/ADEs, including serious or significant non-serious AEs, since consent was signed.
- p. Complete the forms below and transcribe to the eCRFs:
  - Screening/Dispensing Visit Form
  - Exit Visit Form (to be used if the subject is discontinued after a subject ID has been assigned in ORS)

### 6.1.2 2-Week Follow-up Visit

The 2-Week Follow-up Visit will proceed as follows:

NOTE: All VA measurements MUST be made using a phoropter.

NOTE: Study lenses should not be dispensed at this visit unless replacement lenses are required. Lenses worn to this visit should be returned to the subject for use until the next scheduled visit.

NOTE: If the subject comes to a visit not wearing lenses due to requiring a replacement and is not experiencing any problems, it is preferred to do an Unscheduled Visit for Product Dispensing Only and reschedule the 2-Week visit within the visit window. Refer to Unscheduled Visit, Section 6.1.5

NOTE: If the subject comes to a visit not wearing lenses and does not require a replacement, reschedule the current visit within the visit window.

- a. If a subject misses the scheduled follow-up visit and cannot be seen prior to the start of the visit window for the next scheduled follow-up visit, then the visit is considered missed.
- b. Collect the following lens wear parameters from the subject, since last visit:
  - Average number of days per week lenses were worn
  - Average number of times rewetting drops used per day on days when lenses were worn
  - Average daily wearing time
  - Average hours of comfortable wear
  - Hours lenses worn on the day of this visit

- c. Collect the Symptoms/Complaints from the subject using the 0-4 rating scales.
- d. Collect the Subjective Assessments from subject using the 0-100 rating scales.
- e. Collect any relevant medical treatment information, including any adverse events, use of concomitant medications and/or culture that may have been taken since the last visit.
- f. Evaluate the lenses (while on eye) and record the following assessments:
  - Distance lens VA
  - Over-refraction and distance VA
  - Lens wettability
  - Lens discoloration
  - Lens deposits (type, percent and degree)
  - Lens centration
  - Lens movement
  - For each eye, compare the high contrast distance lens VA to the high contrast distance lens VA obtained at the Screening/Dispensing Visit. If the VA has decreased by 10 letters (0.2 logMAR) or more, explain.
- e. Perform a slit lamp examination (remove and store the lenses in the appropriate disinfecting solution during the exam, either Biotrue multi-purpose solution or Boston SIMPLUS Multi-Action Solution) and record the following in subject source documents for entry in to EDC:
  - Any ungraded finding marked as "Present"
  - Any new corneal scars
  - Any neovascularization within the central 6 mm of the cornea
  - Any corneal staining
  - Any corneal infiltrate (record details on the APPENDIX C: Corneal Infiltrates Evaluation Form)
  - Record and sketch any scars and slit lamp findings greater than Grade 2 in the subject's source document.
- g. Return the lenses to the subject to wear until the final study visit.
- h. If the subject needs to exit the study at this visit, complete the Exit Visit as per Section 6.1.4.
- i. Complete the forms below and transcribe to the eCRFs.
  - 2-Week Follow-up Visit Form
  - Exit Visit Form (to be used if the subject is discontinued or exited at this visit)

### 6.1.3 1-Month Follow-up

The 1-Month Follow-up will proceed as follows:

NOTE: All VA measurements MUST be made using a phoropter.

NOTE: If all scheduled visits are performed on time and the subject completes the 1-Month Visit, the Exit Visit will be done at the same time.

NOTE: If the subject comes to a visit not wearing lenses due to requiring a replacement and is not experiencing any problems, it is preferred to do an Unscheduled Visit for Product Dispensing

Only and reschedule the 1-Month visit within the visit window. Refer to Unscheduled Visit, Section 6.1.5.

NOTE: If the subject comes to a visit not wearing lenses and does not require a replacement, reschedule the current visit within the visit window.

- a. Collect the following lens wear parameters from the subject, since last visit:
  - Average number of days per week lenses were worn
  - Average number of times rewetting drops used per day on days when lenses were worn
  - Average daily wearing time
  - Average hours of comfortable wear
  - Hours lenses worn on the day of this visit
- b. Collect the Symptoms/Complaints from the subject using the 0-4 rating scales.
- c. Collect the Subjective Assessments from subject using the 0-100 rating scales.
- d. Collect any relevant medical treatment information, including any adverse events, use of concomitant medications and/or culture that may have been taken since the last visit.
- e. Evaluate the lenses (while on eye) and record:
  - Distance lens VA
  - Over-refraction and distance VA
  - Lens wettability
  - Lens discoloration
  - Lens deposits (type, percent, and degree)
  - Lens centration
  - Lens movement
  - For each eye, compare the high contrast distance lens VA to the high contrast distance lens VA obtained at the Screening/Dispensing Visit. If the VA has decreased by 10 letters (0.2 logMAR) or more, explain.
- f. Perform a slit lamp examination (remove and store the lenses in the appropriate disinfecting solution during the exam, either Biotrue multi-purpose solution or SIMPLUS Multi-Action Solution) and record the following:
  - Any ungraded finding marked as "Present"
  - Any new corneal scars
  - Any neovascularization within the central 6 mm of the cornea
  - Any corneal staining
  - Any corneal infiltrate (record details on the APPENDIX C: Corneal Infiltrates Evaluation Form)
  - Record and sketch any scars and slit lamp findings greater than Grade 2 in the subject's source document.
- f. Complete the forms below and transcribe to the eCRFs.
  - 1-Month Follow-up Visit Form

NOTE: Do not continue with the Exit Visit until/unless the subject is ready to exit the study. Subjects who require further follow-up at the conclusion of the 1-Month

Follow-Up Visit will be followed according to the AE and/or Unscheduled Visit Section until the AE is resolved or stabilized

#### 6.1.4 Exit Visit

## The Exit Visit will proceed as follows:

- a. Indicate status of the subject on the Exit Visit Form. If the status is "Discontinued" (dispensed or non-dispensed), indicate the (one) PRIMARY exit reason for each eye on the Exit Visit Form.
- b. Collect any relevant medical treatment information, including any adverse events, use of concomitant medications and/or culture that may have been taken since the last visit.
- c. For all subjects, complete an exit ocular examination without lenses on the eyes. Collect the following assessments:
  - Spherocylindrical refraction
  - High contrast distance best spectacle-corrected visual acuity (BSCVA)
  - Keratometry

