## 3.2.3 Subject Discontinuation

A subject MAY be discontinued (at the discretion of the Investigator, the Sponsor, and/or the IRB) prior to the final study visit for a variety of reasons, including, but not limited to:

- An adverse event (AE) occurring during the course of the study, which precludes continued treatment or follow-up
- Persistent Grade 3 or 4 slit lamp findings (must be reported to the Sponsor within 24 hours)
- Persistent study-related symptoms/complaints

A subject MUST be discontinued prior to the final study visit (1-Month Visit [Visit 3]) for any of the following reasons:

- Voluntary withdrawal
- Death
- Investigator decision that it is not in the best medical interest of the subject to continue participation in the investigation
- Ineligible at screening/dispensing a subject who was enrolled but was later found to have not met the eligibility criteria
- Inability to maintain recommended wearing and rewetting drop schedule
- Continued failure to follow subject instructions
- Lack of motivation
- Lost to follow-up (refer to Section 3.2.4)
- Instillation of non-medically indicated solution not specified in the protocol
- Other eve is discontinued
- Becomes pregnant during the study

Prior to discontinuing a subject, every effort should be made to contact the subject, schedule an Exit Visit, obtain as much follow-up data as possible, and retrieve all study materials. Adverse events will be followed as described in Section 7.0. Subject discontinuations will be documented clearly on the source document and applicable electronic case report form (eCRF). The Investigator should indicate the PRIMARY (one) reason that the subject was discontinued for each eye. Subjects who are discontinued from the study following randomization will not be replaced.

Exit Visit assessments should be completed for discontinued subjects.

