## d. For each eye:

- Compare the final visit high contrast distance BSCVA to the high contrast distance BSCVA obtained at the Screening/Dispensing Visit. If the VA has decreased by 10 letters (0.2 logMAR) or more, explain.
- Compare the final visit keratometry readings to the Screening/Dispensing Visit keratometry readings. If there is a change of 1.00 D or more, explain.
- e. Indicate if there were any changes to pre-existing corneal scars.
- f. Collect all dispensed lenses (worn and unworn) and Study Kit(s) from the subject and return all to the Sponsor or designee using the return materials provided (refer to Section 4.5). Worn lenses will be returned in lens cases filled with Bausch + Lomb Sensitive Eyes Saline Solution.
- g. Complete the forms below and transcribe to the eCRFs.
  - Exit Visit Form

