### NOTE: All VA measurements MUST be made using a phoropter.

- a. Determine the reason for the Unscheduled Visit.
  - If the visit is to dispense study materials only and the subject is not experiencing any problems, refer to Product Dispensing Only, Section 6.1.5.1.
  - If the subject is experiencing problems, proceed with the Unscheduled Visit assessments as needed, below.
- b. Collect the following lens wear parameters from the subject, since last visit:
  - Average number of days per week lenses were worn
  - Average number of times rewetting drops used per day on days when lenses were worn
  - Average daily wearing time
  - Average hours of comfortable wear
  - Hours lenses worn on the day of this visit
- c. Collect the Symptoms/Complaints from the subject using the 0-4 rating scales.
- d. Collect the Subjective Assessments from the subject using the 0-100 rating scales.
- e. Collect any relevant medical treatment information, including any adverse events, use of concomitant medications and/or culture that may have been taken since the last visit
- f. If the subject did not come to the visit wearing one or more study lenses, go to step g. Otherwise, evaluate the lenses (while on eye) and record the following assessments:
  - Distance lens VA
  - Over-refraction and distance VA
  - Lens wettability
  - Lens discoloration
  - Lens deposits (type, percent and degree)
  - Lens centration
  - Lens movement
  - For each eye, compare the high contrast distance lens VA to the high contrast distance lens VA obtained at the Screening/Dispensing Visit. If the VA has decreased by 10 letters (0.2 logMAR) or more, explain.
- g. Perform a slit lamp examination (remove and store the lenses in the appropriate disinfecting solution during the exam, either Biotrue multi-purpose solution, or SIMPLUS Multi-Action Solution) and record the following:
  - Any ungraded finding marked as "Present"
  - Any new corneal scars
  - Any neovascularization within the central 6 mm of the cornea

- Any corneal staining
- Any corneal infiltrate (record details on the APPENDIX C: Corneal Infiltrates Evaluation Form)
- Record and sketch any scars and slit lamp findings greater than Grade 2 in the subject's source document.
- g. If additional study rewetting drops are required at this visit, log into ORS to dispense a new Study Kit (refer to Section 4.4.2) to the subject according to ORS and InForm and record in the Product Accountability Log.

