#### 8.6.1.2 Graded Slit Lamp Findings

At each follow-up visit, graded slit lamp findings will be assessed for each eye using Grades 0 through 4. Using only the non-missing observations from all visits without imputation, each eye will be classified with respect to findings greater than grade 2 at any visit (Absent, Present). Missing data will not be imputed. Greater than grade 2 findings (Absent, Present) will be summarized at the eye level by treatment using categorical summary statistics for the Safety Set in a table. A one-sided upper 95% confidence limit around the difference in "Present" proportions between the test and control treatment groups will be constructed using the Newcombe-Wilson score method. If the upper confidence limit is less than 5.0%, then the null hypothesis that the test solution is not non-inferior will be rejected, and the test solution will be statistically successful in this outcome.

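### The Exit Visit list in Section 6.1.4 has no graded slit lamp examination, so a subject seen last at a stand-alone early exit leaves without a grade for the primary safety endpoint

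*Combined protocol and SAP*

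**What the plan says.** Section 3.2.3 (Subject Discontinuation) asks sites to "schedule an Exit Visit, obtain as much follow-up data as possible, and retrieve all study materials" before a subject is discontinued, and adds: "Exit Visit assessments should be completed for discontinued subjects". The Exit Visit set is the only set of assessments named there.

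Section 6.1.4 (Exit Visit), step c, reads "For all subjects, complete an exit ocular examination without lenses on the eyes. Collect the following assessments". The list that follows is spherocylindrical refraction, high contrast BSCVA and keratometry. Step e adds "Indicate if there were any changes to pre-existing corneal scars". The remaining steps cover exit status, adverse events and medications, comparisons with the Screening/Dispensing Visit, return of materials and forms. No step asks for graded slit lamp findings.

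Other routes out of the study differ:

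- **2-Week visit (6.1.2).** The slit lamp examination comes first, and then "If the subject needs to exit the study at this visit, complete the Exit Visit as per Section 6.1.4".
- **1-Month visit (6.1.3).** The slit lamp examination is part of the visit, and the Exit Visit is done alongside it.
- **Unscheduled Visit (6.1.5).** A slit lamp examination is listed, but for a subject with problems the site is told to "proceed with the Unscheduled Visit assessments as needed".

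Section 8.6.1.2 (Graded Slit Lamp Findings) classifies each eye as having or not having a finding above grade 2 "Using only the non-missing observations from all visits without imputation". This is the only primary safety endpoint (Section 8.1.1).

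**The concern.** A site that follows Sections 3.2.3 and 6.1.4 exactly can exit a subject at a stand-alone visit, lenses off and subject present, without recording the one measurement that the primary safety endpoint needs. Nothing is imputed, so the consequence depends on timing. A subject who leaves before the 2-Week visit has no follow-up grade and falls out of the analysis. A subject who leaves later is classified from the earlier examination only, and a finding that arose since then is not counted.

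The missing grades may be informative. Section 3.2.3 lists adverse events and persistent study-related symptoms among the reasons for discontinuation, and both could plausibly go with slit lamp findings. If they were more frequent in the Test arm, the unexamined eyes would lower the observed Test rate and so favour a finding of non-inferiority.

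**Working it through.** **1. Size of the group that could be affected.** Section 8.3.5 wants 160 completers per arm and allows 13% losses: 160 / (1 − 0.13) = 183.9, rounded to 184. The plan's figure is reproduced. The allowance is 184 − 160 = 24 subjects, or 48 eyes, per arm. This is an upper bound for the present purpose. It includes subjects lost to follow-up, who attend no exit visit, and subjects who exit at a scheduled visit, who are examined. The documents do not say how many would leave through a stand-alone Exit Visit.

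**2. What each route yields.**

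| Last contact | Graded slit lamp at that contact |
|---|---|
| 2-Week visit with exit | Yes, under 6.1.2 |
| 1-Month visit with exit | Yes, under 6.1.3 |
| Unscheduled Visit with exit | Listed, as needed |
| Stand-alone Exit Visit | Not listed in 6.1.4 |
| Exit at Screening/Dispensing | Only the screening examination, which precedes the first drop (6.1.1, steps e and j) |

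Stand-alone exits are foreseen: Section 3.1 mentions an early discontinuation visit, and Section 6.1.1 step l mentions exit and early termination visits separately from the 1-Month visit.

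**3. How many hidden findings would reverse the conclusion.** The inputs are the 5-point margin, the one-sided 95% Newcombe-Wilson limit (z = 1.645) and the planned rate of 0.005 per eye (Sections 8.2.1, 8.3.1 and 8.6.1.2). The planned rate gives 320 × 0.005 = 1.6 expected eyes per arm, so the illustration assumes 2 observed in each arm.

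With p_T and p_C the observed proportions, u_T the Wilson upper limit for Test and l_C the Wilson lower limit for Control:

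upper limit = (p_T − p_C) + √[(u_T − p_T)² + (p_C − l_C)²]

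*As observed, 2/320 in each arm.* p = 0.00625, u_T = 0.01871, l_C = 0.00207. The limit is 0 + √(0.01246² + 0.00418²) = 0.0131, or 1.3%. Test passes.

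*All 48 missing eyes per arm now examined (368 eyes per arm), h further findings in Test and none in Control.* Control is 2/368: p_C = 0.00543, l_C = 0.00180.

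- h = 11: Test is 13/368 = 0.03533, u_T = 0.05485. The limit is 0.02989 + √(0.01952² + 0.00363²) = 0.0497, which passes.
- h = 12: Test is 14/368 = 0.03804, u_T = 0.05810. The limit is 0.03261 + √(0.02006² + 0.00363²) = 0.0530, which fails.

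So 12 of 48 unexamined Test eyes (25%) would need a finding, with none in the unexamined Control eyes. At the planned rate the expected number among 48 eyes is 48 × 0.005 = 0.24.

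**The case against.** **The Exit Visit is mostly an add-on.** At the 2-Week and 1-Month visits the slit lamp comes first, and the note under Appendix A says the Exit column is performed in addition to the visit's own procedures. This stands, and it confines the gap to stand-alone exits and to Unscheduled or Dispensing Visits where no examination after exposure is made.

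**Other wording may cover it.** Section 3.2.3 asks for as much follow-up data as possible, and the scar question in 6.1.4 implies looking at the cornea. Neither names a graded examination, so neither ensures that a grade is recorded. The body of the Appendix A table is not readable in the text available here. That cannot be held against the plan, and its Exit column may include the slit lamp. If so, the list in 6.1.4 still needs to match it.

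**The worst cases are already graded.** A reader might infer that subjects who leave with "Persistent Grade 3 or 4 slit lamp findings" escape the analysis. They will normally have been graded above 2 already, and one recorded grade is enough to classify the eye as having a finding. Staining of Grade 3 or more is also an expedited-report event (Section 7.1.4). This part of the objection stands. The informative-missingness argument rests on other adverse events and on symptoms.

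**Comfort and dryness.** A reader might also infer that the Exit Visit should collect these ratings because they feed the effectiveness endpoints. Sections 8.6.1.3 and 8.6.1.4 average scores over scheduled follow-up visits, the primary analysis uses the PP set without imputation (8.6.7), and the ITT imputation uses scheduled-visit scores. A rating from a stand-alone exit would enter none of these analyses.

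**One or two eyes could decide the endpoint.** This is true only at the edge of the margin. With 320 eyes per arm and 1 Control event, 10 Test events give 4.86% and 11 give 5.24%. But 10 or more events in 320 eyes at a rate of 0.005 has probability of about 6 in a million. From 2 events in each arm, two more Test events (4 against 2) give only 2.2%.

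**Conclusion.** The concern holds for the slit lamp examination at stand-alone early exits. As written, Sections 3.2.3 and 6.1.4 allow a subject to leave without a grade at that point, and Section 8.6.1.2 then omits the eye or relies on an earlier examination. That the eye is omitted before Week 2 assumes the screening examination is not counted as follow-up. If it were counted, the eye would be classified as free of findings on pre-exposure data, since exclusion criterion 12 bars any finding of grade 2 or more at entry.

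This is a completeness point about the sole primary safety endpoint, not a likely reversal of the result. The figure of about 12 in 48 assumes 2 observed events per arm, all 13% losses unexamined, and no hidden Control findings. Whether missingness would in fact differ between arms cannot be judged from the documents. The point does not extend to the effectiveness endpoints. The change is cheap and worth making.

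**What to change.** - **Section 6.1.4, step c:** add the Appendix B graded slit lamp examination for any subject who exits without having had one at that same visit.
- **Section 3.2.3 and the Appendix A Exit column:** align both with step c.
- **Section 8.6.1.2:** state that grades from Exit and Unscheduled Visits count when an eye is classified for a finding at any visit. At present the section speaks of follow-up visits in one sentence and all visits in another, and the synopsis says any follow-up visit.
- **Section 6.1.5, step j:** correct the cross-reference. It sends an exiting subject to Section 6.1.5, which is the Unscheduled Visit itself; the Exit Visit is Section 6.1.4.

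The cost is a protocol wording change, one more field on the Exit form and a few minutes per early leaver. The subject is already on site with lenses removed, and the examination is already done at every scheduled follow-up visit. The counting rule should be settled before unmasking.
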